While, to date, there is no gold standard technique established to measure bone perfusion in human patients, dynamic contrast-enhanced MRI (DCE-MRI) is the imaging modality that has been used most frequently and effectively to measure bone perfusion in patients without metal implants implants¹⁶⁻²¹. Because of this, developing a better understanding of the relationship between DCE-MRI, which assesses the bone and surrounding soft tissues in a three-dimensional format and ICG-based DCE-FI, which is surface-weighted, is an important next step. Data acquired from intraoperative DCE-MRI and DCE-FI will be used to create a fluorescence-imaging specific model which will correct for the surface-weighted nature of fluorescence imaging and more accurately reflect the fluorescence intensity and kinetics throughout the entire depth of the bone.

There are currently no accepted intraoperative tools that can be used to make objective decisions about bone perfusion. Methods currently used to guide debridement are quite rudimentary. Clinical judgement is based on the gross appearance of soft tissue and bone, including color, turgor, and extent of soft tissue stripping. A burr may be used to look for bleeding bone. More extensive debridement is thought to minimize risk of index infection or reduce the rate of persistent infection; however, this comes at the cost of increasingly complex reconstructive procedures to fill bony defects^{22 23, 24}. Clearly what is needed is a functional imaging system which can assess vascular perfusion of surgical field tissue to guide surgeons in the amount of tissue to debride. In turn, this will lead to fewer infections and a more effective treatment of SSIs at the fracture site. Both scenarios will allow patients to return to duty or work sooner.

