7.1 Sample Size Determination

The participating Statisticians on the study are members of the Norris Cotton Cancer Center and/or Department of Orthopaedics at Dartmouth-Hitchcock Medical Center. Sample size determination is based on the primary objective of the study as a pilot assessment of ICG fluorescence intensity of bone perfusion.

For patient cohort 1, we anticipate that approximately 10% of patients with open fracture will have an SSI within 12 months of their fracture^{1, 2, 32}. A total sample size of 160 patients will result in an estimated 16 patients with an SSI and 144 patients without an SSI. We will have 86% statistical power to detect a mean maximum fluorescence intensity (I_{max}) difference of 24 (a.u.) between the SSI group and the non-SSI group with an estimated standard deviation of 30 (a.u.) and 15 (a.u.), respectively. All parameters were obtained from our previous porcine study. To be conservative, we increased the standard deviation by 50% for this power calculation. The type I error is set to be 5%. If we assume a drop-out rate of 10%, then a total of 176 patients will be enrolled.

For patient cohort 2, we anticipate approximately 30% of patients with an SSI will go on to develop a persistent SSI/treatment failure within 12 months of diagnosis of their SSI¹². Based on this estimate, a sample size of 22 patients with SSIs and 52 patients without, will have 93% statistical power to detect a mean I_{max} difference of 24 (a. u.) between the persistent SSI/treatment failure group and the non-persistent SSI/non-treatment failure group with I_{max} estimated standard deviation of 30 (a. u.) and 15(a. u.). All parameters are obtained from our previous porcine study, which are consistent with a pilot study conducted at STC in human participants using ICG fluorescence for a different indication. To be conservative, we increased the standard deviation by 50% for this study. The type I error is set to be 5%. If we assume the dropout rate is 10%, then a total of 82 patients will be recruited.

For patient cohort 2-1, the strength of the relationship between DCE-MR and DCE-FI measurements will

be assessed by determining the zero-order correlation and resulting R2 metric. A sample of 21 was estimated utilizing formula presented by Bonett & Wright ³⁶ with a Type I error rate of 0.05 and Type II error

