rate of 0.20 (1-Power) to estimate the magnitude of zero-order correlation and interval estimation. Formula inputs included expected zero-order relationship of $r = 0.85$ (95% CI 0.55 to 1.00). To optimize the imaging parameters of DCE-MRI, extra seven patients has been added into this cohort. Thus, total of 30 patients will be involved in this cohort.

Patient cohort 3 will serve as the control group for cohorts 1 and 2.

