	Unplanned fracture-related reoperation	Binary	Mean perfusion will be lower among patients who require unplanned fracture-related reoperation	Students t-test Multivariable logistic regression

Patient cohort 2:

For the primary outcome, treatment failure will be the dependent variable and bone and tissue perfusion, as measured by ICG fluorescence will be the independent variable. Descriptive statistics, including means and standard deviations, will be presented with 95% confidence intervals. To select the most important ICG fluorescence kinetic curve-related variables, we will perform a bivariate analysis evaluating whether each variable predicts infection and we will select the variable with the highest area under the curve (AUC).

Our primary null hypothesis is that the post-debridement maximum ICG intensity ($I_{max-post}$) among patients with persistent SSI/treatment failure is equal to or greater than that in the non-persistent SSI/non-treatment failure patient group. The primary alternative hypothesis is that $I_{max-post}$ in the persistent SSI/treatment failure

group is smaller than that in the non-persistent SSI/non-treatment failure group. We will then perform a Students t-test to determine the association between the most important ICG fluorescence variable and persistent SSI/treatment failure. A p-value of 0.05 or less will be considered significant for differences between persistent SSI/treatment failure and non-persistent SSI/non-treatment failure groups.

We will then apply multiple logistic model including ICG fluorescence and previously identified predictors for persistent SSI/treatment failure³⁷⁻³⁹. Wald test will be used to determine if ICG fluorescence or any other predictors are significant in the model. We set the type I error at 5%. Table 7.2 shows a summary of the study outcome, corresponding hypotheses and method of analysis to be performed. We anticipate that we will demonstrate a statistically significant difference between the maximum post-debridement ICG fluorescence in patients who fail treatment for their SSI resulting in persistent SSI/treatment failure and those who do not.

For subset cohort 2-1, for each DCE-MR and DCE-FI parameter, statistics of median and percentiles will be calculated for each of ROIs. Due to the small cohort size, the correlations between DCE-MRI and DCE-FI will be utilized to analyze the data of each corresponding ROI, assuming that all ROIs in each subject were independent⁴⁰.

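### The DCE-MRI subset treats regions of interest from one patient as independent, so the interval for the MRI-fluorescence correlation is likely too narrow

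*Combined protocol and SAP*

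**What the plan says.** Section 7.1 plans the MRI subset (cohort 2-1) in patients. The relation between the two modalities will "be assessed by determining the zero-order correlation and resulting R2 metric". The sample of 21 is meant "to estimate the magnitude of zero-order correlation and interval estimation", with an expected r of 0.85 and a 95% interval of 0.55 to 1.00. After patients are added for tuning the MRI parameters, a "total of 30 patients will be involved in this cohort".

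Section 7.2 then changes the unit of analysis. It opens with the reason, "Due to the small cohort size", and says that "the correlations between DCE-MRI and DCE-FI will be utilized to analyze the data of each corresponding ROI", "assuming that all ROIs in each subject were independent". Reference 40 is attached to that sentence.

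Neither section gives the number of ROIs per patient or an ICC. Neither names a mixed model, a cluster-robust interval, a patient-level bootstrap or a patient-level sensitivity analysis for this subset. Section 1.1 adds that the paired imaging data "will be used to create a fluorescence-imaging specific model", which is to correct for the surface weighting of fluorescence.

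**The concern.** A small cohort explains why one would like more data points. It is not evidence that several ROIs from one patient carry independent information. Section 6 (Surgical Procedures) shows what they share: one DCE-MRI acquisition, one ICG injection per imaging series, and an arterial input function measured at the patient's finger during that injection. They also share the patient's circulation and injury. Positive correlation within patients is therefore to be expected in both modalities.

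An interval that counts each ROI as a separate observation then claims more information than 21 or 30 patients provide. The size of the correlation with its interval is what this subset is meant to deliver, so the error falls on its main output.

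**Working it through.** **1. The plan's own figure.** The stated inputs are r = 0.85, 95% interval 0.55 to 1.00, type I error 0.05, type II error 0.20 and n = 21. A Fisher-z comparison of 0.55 with 0.85 uses n = ((z_α + z_β) / (atanh 0.85 − atanh 0.55))² + 3.

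- Two-sided: ((1.960 + 0.842) / (1.256 − 0.618))² + 3 = 22.3, so 23.
- One-sided: 18.2, so 19.

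The stated 21 lies between these. A precision formula, n = 4(1 − r²)²(1.96/w)² + 3 with full width w = 0.45, gives 8.8, so 9 (12 after a second-stage correction). Whichever route was used, 21 is a count of patients.

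**2. Interval with one value per patient.** The limits are tanh(atanh r ± 1.96/√(n − 3)). At r = 0.85 this gives 0.66–0.94 for 21 patients and 0.71–0.93 for 30.

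**3. Interval with all ROIs counted as independent.** With N patients and m ROIs each, the standard error on the z scale is 1/√(Nm − 3). For N = 21 and m = 5, Nm = 105, the standard error is 1/√102 = 0.099 and the interval is 0.79–0.90.

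**4. Effect of clustering.** If both modalities have the same ICC, and the correlation is the same between and within patients, the variance of Fisher z grows by about

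DE = 1 + (m − 1) × ICC².

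For m = 5 and ICC 0.5, DE = 1 + 4 × 0.25 = 2.00, so the standard error should be √2.00 = 1.41 times larger (1.39 in simulation). For m = 10 and ICC 0.7, DE = 1 + 9 × 0.49 = 5.41, a factor of 2.33 (2.33 in simulation).

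**5. Coverage of the nominal 95% interval.** The simulation used bivariate normal patient and ROI effects, 21 patients, true r = 0.85 and 20,000 trials per setting. The values of m and ICC are assumptions.

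| ICC, both modalities | 3 ROIs | 5 ROIs | 10 ROIs |
|---|---|---|---|
| 0.1 | 95% | 95% | 94% |
| 0.3 | 93% | 91% | 86% |
| 0.5 | 89% | 84% | 72% |
| 0.7 | 83% | 74% | 60% |

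With 30 patients every figure is within one point, so more patients do not cure it. Mean pooled r was 0.846–0.850, so the estimate itself is essentially unbiased.

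**6. Intervals around r = 0.85, 21 patients.**

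| Setting | As planned | With the true spread |
|---|---|---|
| 5 ROIs, ICC 0.5 | 0.79–0.90 | about 0.76–0.91 |
| 10 ROIs, ICC 0.7 | 0.81–0.88 | about 0.73–0.92 |

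**7. Other patterns** (coverage at 3 / 5 / 10 ROIs, 21 patients, r = 0.85).

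- ICCs 0.3 and 0.1: 94 / 93 / 92%.
- ICCs 0.5 and 0.2: 93 / 91 / 87%.
- Only one modality clustered, ICC 0.2 and 0, within-patient correlation 0.95: 90 / 85 / 75%, with mean r 0.851–0.854.
- Between- and within-patient correlations unequal (30 patients, 4 ROIs, ICC 0.5): about 90% when they are 0.95 and 0.75, and 79% when they are 0.75 and 0.95.

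**8. If r = 0 were tested.** The plan names no such test for this subset. If one were run on pooled ROIs, its type I error would be 5 / 5 / 6% at ICC 0.1, 11 / 16 / 27% at 0.5 and 17 / 26 / 41% at 0.7.

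**The case against.** Five points can be made for the plan.

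- **Reading.** The text may mean one correlation per ROI position, with one value per patient in each. There would then be no inflation. But the independence assumption would also serve no purpose, so pooling is the more natural reading. The sentence needs editing on either reading.
- **No interval is named in Section 7.2.** That is true: interval estimation appears in Section 7.1 as the aim of the sample size. The Fisher-z interval used above is the ordinary choice, not one the plan states.
- **A reference supports the sentence.** By its title it is a text on nonparametric methods for longitudinal data. It was not available for this review. It may mean that a rank correlation is intended, but pooling ROIs under an independence assumption raises the same issue there.
- **The ICC may be low.** Section 1.2 reports large differences between ROIs in the porcine model, which points that way, although those injuries were induced. At ICC 0.1 the effect is negligible.
- **The planned precision is still met.** This stands. Even the one-value-per-patient intervals (0.66–0.94 and 0.71–0.93) lie inside 0.55–1.00 if r is near 0.85.

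Section 1.1 also says that the imaging data, not the interval, will feed the depth-correction model, so no harm to that model has been shown. These points limit the size of the problem. None of them supports the assumption.

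**Conclusion.** The concern holds. The plan adopts an assumption that is unlikely to be true, justifies it by cohort size, and has no adjustment elsewhere. On the natural, pooled reading, the interval for r, and hence for R², is likely too narrow.

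The size depends on two quantities that the documents do not give. Over 3 to 10 ROIs per patient and equal ICCs of 0.1 to 0.7, actual coverage runs from about 95% down to 60%, that is, from negligible to large. What suffers is the stated precision. The estimate of r, the adequacy of the patient numbers for the planned interval, and the primary endpoints are not affected. The change should be made, but the trial does not depend on it.

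**What to change.** In Section 7.2:

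1. Delete the independence assumption, keep all ROIs, and name the patient as the sampling unit.
2. Report r and R² with a bootstrap interval that resamples whole patients, built on the Fisher-z scale with a t multiplier on patients minus 1 degrees of freedom.
3. State how many ROIs each patient contributes, and report the ICC of each modality.
4. If one value per patient in each correlation is what was meant, say so. The assumption can then simply be removed.

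A bivariate mixed model with a patient random effect is an alternative. It gives between- and within-patient correlations separately. These are different quantities from the planned zero-order r, and the model was not checked here at 21–30 patients.

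The cost is SAP wording and a few lines of code, with no new patients or data. The interval becomes wider where ROIs are clustered. Its coverage is closer to nominal but not exact: with 21–30 patients, ICC 0.1–0.7 and 3–10 ROIs, the Fisher-z/t patient bootstrap covered 93–95% and a plain percentile bootstrap 92–94% (2,000 trials, 999 resamples). At ICC 0.1 there is no gain in coverage.

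The subset size should be reconciled in the same edit: 21 + 7 = 28, Sections 6 and 7.1 say 30, and the Study Summary says 38.

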7.3 Subject Population(s) for Analysis

This study will involve consecutive patients 18 years of age or older who present to DHMC with an open fracture will be considered for the open fracture cohort (Cohort 1). Similarly fracture patients who present with an SSI following fracture fixation or joint fusion will be screened for the fracture SSI cohort (Cohort 2). Patients who present to DHMC with a closed fracture will be considered for the closed fracture cohort (Cohort 3). The image and clinical outcome data of all patients involved in this study will be analyzed.

8 Safety and Adverse Events

8.1 IRB Reporting Requirements for Adverse Events & Unanticipated Problems

Adverse events that are serious, unexpected, and possibly, probably or definitely related to participation in the research study will be reported to the Dartmouth Committee for the Protection of Human Subjects (CPHS) and to the sponsor. These events will be reported to the CPHS within 1 week. The sponsor will report these events to the FDA within 7 calendar days. All lethal events will be reported to the CPHS, Sponsor, and FDA.

Adverse events to be reported to the Sponsor are: any adverse experience, defined as any untoward or unfavorable medical occurrence in a human subject, including any abnormal sign (for example, abnormal physical exam or laboratory finding), symptom, or disease, temporally associated with the subject's

participation in research, whether or not considered related to the subject's participation in the research), that is considered:

- Serious: Death; a life-threatening adverse drug experience; inpatient hospitalization or prolongation of existing hospitalization; a persistent or significant disability or incapacity; or a congenital anomaly or birth defect; and
- Unexpected: Any adverse experience, the specificity or severity of which is not consistent with the current investigator brochure or consent form; and
- Possibly related: There is a reasonable possibility that the incident, experience, or outcome may have been associated with the procedures involved in the research; and
- Is experienced by a participant in a trial open at a site subject to review by the CPHS.

An unanticipated problem involving risks to subjects or others is defined as any incident, experience, or outcome that meets each of the following criteria:

- Unanticipated in terms of nature, severity, or frequency given: (a) the research procedures that are described in the protocol-related documents, such as the IRB-approved research protocol and consent document; and (b) the characteristics of the subject population being studied; and
- Possibly related to participation in the research means there is a reasonable possibility that the incident, experience, or outcome may have been associated with research participation; and
- The problem suggests that the research places subjects or others at a greater risk of harm (including physical, psychological, emotional, economic, legal, or social harms) than was previously known or recognized.

Copies of each report and documentation of IRB notification and receipt will be kept in the Clinical Investigator's study file.

Any unexpected or serious adverse events, or drug reaction beyond those expected from open sarcoma surgery that are determined likely to be related to the study procedures, will be reported to the FDA as required.

8.2 Institutional Safety and Data Monitoring

This study will be monitored by the Data Safety Monitoring and Accrual Committee (DSMAC). The Committee meets quarterly to review accrual rates and information for studies that have accrued participants. The Clinical Cancer Review Committee (CCRC) determines the frequency of DSMAC review. The DSMAC has the authority to suspend or to recommend termination to the CCRC of all research activities that fall within its jurisdiction. In the event that a study is suspended or terminated, that information will be forwarded to the CPHS (Dartmouth IRB) office.

9 Data Handling and Record Keeping

9.1 Confidentiality

Information about study subjects will be kept confidential and managed according to the requirements of the Health Insurance Portability and Accountability Act of 1996 (HIPAA). Risk of breach of confidentiality of the medical records and status of participants will be minimized. Databases which are used to store subject-sensitive information are password-protected and encrypted during file/data transfers from viewing terminals. Access will be limited to research team members who have undergone CPHS training at Dartmouth. Whenever possible and practical standard-of-care clinical data used in the research will be de-identified when under analysis.

9.2 Case Report Forms

Study case report forms (CRFs) will be the primary data collection instruments for the study. All data requested on CRFs will be recorded. Any missing data will be explained. If a space on the CRF is left blank because the procedure was not performed or the question was not asked, a written notation will be made. If an item is not applicable to an individual case, written notation will be made. Changes to the CRFs will be initialed and dated.

9.3 Record Retention

Following closure of the study, the investigator will maintain all site study records in a safe and secure location. The records are maintained to allow easy and timely retrieval when needed (e.g., audit or inspection) and, whenever feasible, to allow any subsequent review of data in conjunction with assessment

of the facility, supporting systems, and staff. Upon completion of study analysis, research information is stored in Dartmouth College Records Management off-site storage located at [name]. Documents are shredded on site after 50 years of storage.

10 Clinical Site Monitoring

10.1 On-Site Monitoring

Clinical research monitoring for regulatory compliance and data integrity will be conducted. Internal monitoring is conducted by appropriately trained staff of the Office of Clinical Research and Dartmouth-Hitchcock Medical Center Clinical Trials Office who are not involved in the study. This monitoring will include periodic assessment of the regulatory compliance, data quality, and study integrity. Study records will be reviewed and directly compared to source documents and the conduct of the study will be discussed with the investigator. Monitors may request access to all regulatory documents, source documents, CRFs, and other study documentation for on-site inspection. Direct access to these documents is guaranteed by the investigator, who must provide support at all times for these activities.

10.2 Auditing and Inspecting

The study investigators will permit study-related monitoring, audits, and inspections by the IRB, the sponsor, government regulatory bodies, and university compliance and quality assurance groups of all study related documents (e.g. source documents, regulatory documents, data collection instruments, study data, etc.). The study investigators will ensure the capability for inspections of applicable study-related facilities (e.g. pharmacy, diagnostic laboratory, etc.).

Participation as an investigator in this study implies acceptance of potential inspection by government regulatory authorities and applicable university compliance and quality assurance offices.

11 Ethical Considerations

This study is to be conducted according to US and international standards of Good Clinical Practice (FDA Title 21 part 312 and International Conference on Harmonization guidelines), applicable government regulations and Institutional research policies and procedures.

All subjects for this study will be provided a consent form describing this study and providing sufficient information for subjects to make an informed decision about their participation in this study. See Attachment for a copy of the Subject Informed Consent Form. This consent form will be submitted with the protocol for review and approval by the IRB. The formal consent of a subject, using the IRB-approved consent form, will be obtained before that subject undergoes any study procedure. The consent form will be signed by the subject or legally acceptable surrogate, and the investigator-designated research professional obtaining the consent.

12 Study Finances

12.1 Funding Source

This study is being funded by the Orthopaedics Department at Dartmouth Hitchcock Medical Center.

